12.6. PHYSICAL EXAMINATION

Physical examinations are performed at Open-Label Baseline, Week 14, Week 26 or ET, and End of Study. Any clinically significant abnormalities at screening will be recorded on the medical history form. Any new or worsening clinically significant abnormality at all other visits will be recorded as an AE.

12.7. NEUROLOGICAL EXAMINATION

Neurological examinations will be performed at Open-Label Baseline, Week 14, Week 26 or ET, and End of Study.

Each assessment (i.e. Cranial Nerves, Motor System, Sensory System, Reflexes, Coordination, Gait and Romberg's test) will be summarized using summary statistics for categorical variables (normal/abnormal) at each visit by treatment and overall. All percentages will be based on the number of safety subjects in each DB treatment group.

Shift table for baseline condition vs. the worst result during the treatment period (Abnormal > Normal) will be produced by DB treatment and overall. Percentages will be based on the number of subjects in the safety population. The number of subjects without an assessment at the visit will be noted on the shift table.

12.8. VITAL SIGNS

Vital signs (blood pressure, pulse rate, height, height WHO z-score, weight, BMI, BMI z-score, respiratory rate, and oral temperature) will be monitored at every clinic visit. Respiratory rate and oral temperature will be measured following 5 minutes of supine rest.

At any clinic assessment, orthostatic hypotension (determined by blood pressure measurements only) is defined as having either a ≥ 20 mmHg reduction from supine to standing position in systolic blood pressure (SBP) or ≥ 10 mmHg reduction from supine to standing position in diastolic blood pressure (DBP) or both. Orthostatic tachycardia is defined as heart rate increase ≥ 20 bpm from supine to standing position.

Observed values, change from DB baseline, percent change from DB baseline, change from OL baseline, percent change from OL baseline for each vital sign parameter. will be summarized at each visit by DB treatment and overall.

In addition, the markedly abnormal post-baseline vital signs results will also be summarized for subjects with at least one markedly abnormal value during the treatment period. A listing will be provided for all markedly abnormal vital signs. A shift table will be presented comparing shifts from the baseline visit to Week 26 LOCF. Percentages will be based on the number of safety subjects with a non-missing value for both the baseline and post-baseline visit for the given vital sign. A shift table for BMI classification will also be presented comparing shifts from the baseline visit to Week 26 LOCF.

Parameter (unit)	Age (years old)	Markedly Low	Markedly High
SBP (supine, standing) (mmHg)	6-12	Value ≤ 70 and ≥ 20 decrease from baseline	Value ≥ 120 and ≥ 20 increase from baseline
	13-18	Value ≤ 90 and ≥ 20 decrease from baseline	Value ≥ 135 and ≥ 20 increase from baseline
DBP (supine, standing) (mmHg)	6-12	Value ≤ 40 and ≥ 15 decrease from baseline	Value ≥ 80 and ≥ 15 increase from baseline
	13-18	Value ≤ 50 and ≥ 15 decrease from baseline	Value ≥ 90 and ≥ 15 increase from baseline
Pulse rate (supine, standing) (bpm)	6-10	Value ≤ 60 and ≥ 15 decrease from baseline	Value ≥ 135 and ≥ 15 increase from baseline
	11-18	Value ≤ 50 and ≥ 15 decrease from baseline	Value ≥ 120 and ≥ 15 increase from baseline
SBP orthostatic criteria (mmHg)	~	≥ 20 decrease from supine to standing position	NA
DBP orthostatic criteria (mmHg)	~	≥ 10 decrease from supine to standing position	NA
Pulse rate orthostatic criteria (bpm)	~	NA	≥ 20 increase from supine to standing position

Temperature (°C)	~	NA	Value $\geq 38.3^{\circ}\text{C}$ and $\geq 0.8^{\circ}\text{C}$ increase from baseline
------------------	---	----	---

Note: ~ means that the abnormal range is applicable for all subjects within age group: 6 to 17 years old.

Vital signs data will be provided in a data listing.

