#### **15.3.6.4.** Vital Signs

Vital signs (blood pressure, pulse rate, height, weight, BMI, and respiration rate) will be monitored at every visit. Each vital sign parameter will be summarized at each visit for the observed value and change from baseline. In addition, the markedly abnormal post-baseline vital signs results will also be summarized for subjects with at least one markedly abnormal value during the 26-week treatment period. A shift table will be presented comparing shifts from the baseline visit to end of study. The number and percentage of subjects who experienced orthostatic hypotension at each time point will be summarized.

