4.2. DETERMINATION OF SAMPLE SIZE

This study is projected to enroll up to 330 subjects based on the number of subjects who complete the core study.

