5.2. SECONDARY ENDPOINTS

The secondary endpoints are:

- Clinical laboratory evaluations (serum chemistry, hematology, lipid panel, thyroid function panel, urinalysis, sex hormones).
- Clinical evaluations (vital signs, physical examination, body height and weight, Tanner Staging, and 12-lead ECG).
- Frequency and severity of suicidal ideation and suicidal behavior using the C-SSRS.
- Change in CGI-S score.
- Change in ADHD-RS-IV HV total score.
- Change in the inattentiveness and hyperactivity subscales of the ADHD-RS-IV HV.
- Change in Conners 3-P total score and subscale scores (Oppositional, Cognitive problems, Hyperactivity, and ADHD Index).

- Change in CSHQ total score and 8 subscale scores (bedtime resistance, sleep onset delay, sleep duration, sleep anxiety, night wakings, parasomnias, sleep disordered breathing, and daytime sleepiness).
- Change in WFIRS-P total score and 6 domain scores (family, school learning behavior, life skills, child's self-concept, social activities, and risky activities).
- Symptoms of withdrawal using:
 - PWC score
 - DESS score

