6. GENERAL ASPECTS FOR STATISTICAL ANALYSIS

6.1. GENERAL METHODS

- All analyses and summaries will be produced using SAS[®] version 9.3 (or higher) for windows.
- All statistical summaries will be presented based on the treatment received in the double-blind core study (SEP360-202), called DB treatment. Because the treatment received in SEP360-310 is flexible, the treatment groups for summary in SEP360-310 will be labeled as:
 - placebo / dasotraline flexible,
 - dasotraline 2 mg/day / dasotraline flexible,
 - dasotraline 4 mg/day / dasotraline flexible,
 - dasotraline combined / dasotraline flexible, and
 - total.
- The dasotraline combined group will include those subjects who were treated in SEP360-202 with dasotraline 2 mg/day and dasotraline 4 mg/day.
- Summaries will also be presented by visits (Double-Blind Baseline, Open-Label Baseline, Weeks 1, 2, 4, 6, 10, 14, 18, 22, 26, Week 26 or Treatment Period LOCF,

and EOS). See the details for the DESS and PWC for discussion of the display of visits for those summaries.

- Unless otherwise specified, continuous variables will be summarized with descriptive statistics including: n, arithmetic mean, standard deviation (SD), 95% confidence interval for the mean, median, minimum, and maximum values. All categorical/qualitative data will be presented using frequency counts and percentages. Shift tables will be produced for some assessments and will contain counts and percentages of subjects in each cross-classification level of baseline versus post-baseline assessment. Only subjects with a non-missing value for both baseline and post-baseline, at a given visit, will be included in these tables.
- The listings will be provided using the enrolled population (defined in [Section 8.1](#)). For listings related to analyses conducted using the intent-to-treat population, a flag will be shown in the subject column identifying subjects who were excluded from the intent-to-treat population. In general, the subject listings will be sorted by the treatment group, subject number and assessment date (and time, if applicable).

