10. DEMOGRAPHICS AND OTHER BASELINE CHARACTERISTICS

10.1. DEMOGRAPHICS AND OTHER BASELINE CHARACTERISTICS

Demographics (collected at enrollment into the SEP360-202 study) (sex, race, ethnicity, age [years], age group [6-9 and 10-12 years], weight [kg], height [cm], body mass index [BMI, kg/m²], and World Health Organization (WHO) z-scores and percentiles for height and BMI) will be summarized by DB treatment and overall for the safety and ITT populations. These values will be referred to as DB baseline values.

The age, age group [6-9 and 10-13 years], weight, height, BMI, and WHO percentiles for height and BMI at the time of enrollment into the SEP360-310 study will be summarized by DB treatment and overall for the safety and ITT populations. These values will be referred to as OL baseline values. Note that some subjects who were 12 years old at entry into SEP360-202 had turned 13 years old at the time of entry into SEP360-310.

Sex, race, age group, and ethnicity will be summarized by using summary statistics for categorical variables (frequencies and percentages). Percentages for sex, race, age group, and ethnicity will be based on the number of subjects within a DB treatment group. The DB baseline and OL baseline values for Age, height, height percentile, weight, BMI, and BMI percentile will be summarized by using summary statistics for continuous variables (number of subjects, arithmetic mean, standard deviation, 95% confidence interval for mean, median, minimum and maximum values).

Age will be calculated as the number of years between date of birth and date of enrollment into the SEP360-202 and SEP360-310 studies.

$$\text{BMI (kg/m}^2\text{)} = \text{Weight(kg)} / (\text{Height(m)})^2$$

Normal age and sex-based percentiles for weight, height, and BMI will be determined using the WHO growth charts.

BMI category: Underweight (< 5 percentile), Normal (≥ 5 - < 85 percentile), Overweight (≥ 85 - < 95 percentile), Obese (≥ 95 percentile).

A listing of demographic data will be provided for the enrolled population.

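### SAP 12.8 asks for percent change in height and BMI z-scores, where it is undefined at zero, unstable near zero and wrong in sign below zero

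*SAP*

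**What the plan says.** SAP 12.8 opens with the list of parameters: "Vital signs (blood pressure, pulse rate, height, height WHO z-score, weight, BMI, BMI z-score, respiratory rate, and oral temperature". It then calls for observed values, change from the double-blind (DB) baseline, "percent change from DB baseline, change from OL baseline, percent change from OL baseline for each vital sign parameter", at each visit, by DB treatment and overall. Neither document exempts the z-scores or says what to do with a zero or negative denominator.

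Under SAP 6.1, "continuous variables will be summarized with descriptive statistics including: n, arithmetic mean, standard deviation (SD), 95% confidence interval for the mean", followed by median, minimum and maximum. A percent change is a continuous variable, so by default it would be given a mean and a confidence interval.

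Protocol 15.3.6.4 asks for less: "Each vital sign parameter will be summarized at each visit for the observed value and change from baseline". Percent change is therefore an addition made in the SAP.

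Height and weight belong to a secondary endpoint in SAP 5.2: "Clinical evaluations (vital signs, physical examination, body height and weight, Tanner Staging, and 12-lead ECG".

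**The concern.** Percent change is meaningful for a quantity with a true zero that stays positive, such as weight. A z-score is a signed distance from a reference median, and its zero is an ordinary value in the middle of the scale. Dividing by it causes three faults:

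- no value at all when the baseline is 0;
- very large values of either sign when the baseline is close to 0;
- a reversed sign whenever the baseline is negative, so that a falling child shows a positive percent change and a recovering child a negative one.

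Raw height and weight normally rise over half a year in children aged 6 to 13, so the z-scores are the parameters in this list that adjust growth for age. The markedly abnormal criteria in SAP 12.8 include nothing for height, weight, BMI or z-scores, so the change summaries carry much of the growth information. Someone scanning those tables could take the wrong direction from the percent-change rows.

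There are many such rows. Two z-scores, two baselines and ten time points (the nine scheduled treatment weeks plus Week 26 LOCF) make 2 x 2 x 10 = 40 summaries in each of the five columns named in SAP 6.1, leaving the end-of-study visit aside.

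**Working it through.** The plan gives no figure on this point, so there is none to reproduce. The check has two parts.

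**1. Arithmetic, with no assumption.** Percent change = 100 x (follow-up - baseline) / baseline.

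| Baseline z | Follow-up z | Change | Percent change |
|---|---|---|---|
| +1.0 | +0.7 | -0.30 | -30% |
| -1.0 | -1.3 | -0.30 | +30% |
| -0.5 | -0.8 | -0.30 | +60% |
| +0.05 | -0.25 | -0.30 | -600% |
| -0.05 | -0.35 | -0.30 | +600% |
| 0 | -0.30 | -0.30 | undefined |
| -1.0 | -0.7 | +0.30 | -30% |
| -0.5 | -1.0 | -0.50 | +100% |

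The first six rows are the same loss of 0.30. Absolute change reads -0.30 each time; percent change takes five different values, with both signs, and once no value at all.

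**2. Effect on group summaries, under assumed inputs.** The documents give no z-score distribution, so all of these are assumptions:

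- baseline z normal with SD 1.1 and mean -0.4, 0 or +0.4;
- change in z normal with mean -0.25 and SD 0.3, independent of baseline;
- group size 110, which is the projected maximum of 330 (SAP 4.2) divided equally over the three core-study arms in SAP 6.1 (330 / 3 = 110), and 330 for the total column.

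The share of children starting below zero is Phi(-mean / 1.1): Phi(0.364) = 64%, Phi(0) = 50% and Phi(-0.364) = 36%. About 7% of children have a baseline within 0.1 of zero.

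Simulated groups (20,000 of size 110 and 8,000 of size 330):

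| Assumed baseline mean | n | Mean percent change, central 95% range | Mean is positive | Within-group median, average | Median is positive |
|---|---|---|---|---|---|
| -0.4 | 110 | -403% to +486% | 57% | +9% | 96% |
| 0 | 110 | -440% to +439% | 50% | 0% | 50% |
| +0.4 | 110 | -413% to +420% | 43% | -9% | 4% |
| -0.4 | 330 | -484% to +428% | 58% | +9% | >99% |
| 0 | 330 | -479% to +427% | 51% | 0% | 50% |
| +0.4 | 330 | -470% to +420% | 43% | -9% | <1% |

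The true mean change is a fall in every row. The range of the mean does not narrow when n triples, because a few near-zero denominators drive it. The median is stable, but its sign depends on where the group's baselines lie rather than on the direction of change.

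For comparison, mean absolute change in groups of 110 has standard error 0.3 / sqrt(110) = 0.029 and a central 95% range of about -0.31 to -0.19. It was negative in every simulated group of either size.

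**The case against.** The strongest reply is that the right analysis is already in the plan. The sentence that asks for percent change also asks for observed values and absolute change from both baselines, for the same z-scores, at every visit. SAP 12.8 adds raw height, weight and BMI, a BMI-classification shift table to Week 26 LOCF, and a full data listing. The study is single-arm and descriptive, no inference is planned, and no criterion or decision rests on percent change. All of this stands, and it limits the point to misleading rows placed beside valid ones.

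The reply is also right about the simulation. Its inputs are assumed, and the width of the range for the mean reflects a few children rather than an effect size. The SAP reports medians too, and with a baseline mean of +0.4 the median has the right sign in about 96% of groups of 110. That protection is lost at a mean of 0 and reverses at -0.4. The arithmetic in the first table needs none of these inputs.

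The table shells are an attachment that is not available here, and they may omit these rows. The SAP text still says each parameter.

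Two stronger readings are tempting. A reader might infer that the plan would hide or reverse a growth-suppression finding. The documents do not support that, because the absolute-change summaries show the correct direction. Nor do they describe a paediatric growth signal: the weight decreases in Protocol 4.3 come from adults treated for 4 weeks. A reader might also extend the point to oral temperature, whose Celsius zero is arbitrary. Body temperatures are well above zero, so its percent change can neither reverse sign nor become unstable, and temperature is not part of this point.

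**Conclusion.** The point holds as a defect in one specification. As written, SAP 12.8 calls for a statistic that is undefined, unstable or wrong in sign for two of its listed parameters. The sign reversal is certain for any child with a negative baseline z and rests on no assumption. How often a group summary would mislead depends on the baseline distribution, which the documents do not give. Over assumed baseline means from -0.4 to +0.4, with a true mean fall of 0.25, the group mean percent change is positive in about 43% to 58% of groups, and its within-group median averages between +9% and -9%.

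The consequence is limited to descriptive output that could be misread. No sample size, error rate or primary result is affected, and the valid growth summaries remain. It is worth correcting because the rows are wrong rather than merely redundant.

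**What to change.** Add one sentence to SAP 12.8: percent change will not be calculated for height WHO z-score or BMI z-score, for which observed value and absolute change from the DB and OL baselines will be presented. Check the vital-sign table shells against it.

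The cost is that sentence and the removal of some table rows. No new data or analysis is needed, and nothing departs from the protocol, which asks only for observed value and change.

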TEAE	Treatment-emergent adverse event
UDS	Urine drug screen
WFIRS-P	Weiss Functional Impairment Rating Scale – Parent Report
WHODRUG	World Health Organization drug dictionary

**Table 4:** Definition of Key Study Terms

Terms	Definition of terms		
CRF	A printed, optical, or electronic document designed to record all of the protocol required information to report to the Sponsor for each study subject.		
Study Drug (or Study medication)	Term to cover investigational drug.		
Treatment Period	The period of the study in which the study drug is administered.		
Completed Subject	Any subject who participated throughout the duration of the study, up to and including the last on-treatment visit (Week 26).		
Early Termination Subject	Any subject who was successfully screened and enrolled into the treatment period of the study, but did not complete the study.		
End of Treatment	The day that the subject receives protocol-defined last dose of the study drug.		
End of Study	The day that the subject completes the study per the study design.		

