#### 15.3.6.2. Clinical Laboratory Assessments

The laboratory results collected in conventional units will be converted to SI units for the summaries.

Clinical laboratory test results (hematology, chemistry, lipid panel, thyroid function panel, sex hormones, and urinalysis) and their changes from baseline will be summarized by visit using descriptive statistics. Shift tables comparing laboratory test results from OL baseline to end of study will be presented. In addition, the markedly abnormal post-baseline laboratory results will be summarized for certain laboratory tests.

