6.2.3. Missing Data and Last Observation Carried Forward (LOCF)

Methods for handling missing item responses on the questionnaire instruments (i.e. ADHD-RS-IV HV, Conners 3-P, and WFIRS-P) are described in different sections later on.

If a subject discontinues the study prematurely, the last available data (excluding early termination visit assessments if done more than 3 days after the last dose of study medication, unscheduled assessments after the early termination assessment if done more than 3 days after the last dose of study medication, and Withdrawal Period assessments) will be carried forward to the study endpoint (i.e. the LOCF approach) at Week 26. Visits earlier than the early termination date for subjects who discontinued the study prematurely will be included in the LOCF process, even if they are more than 3 days after the last dose of study medication.

The AE and concomitant medication start/end dates will be imputed based on the rules described in [Appendix 3](#).

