12.2. LABORATORY EVALUATIONS

The following laboratory tests are planned to be performed:

HEMATOLOGY: (Differential reported as % and absolute value)

Hemoglobin, Hematocrit, Platelet Count, red blood cell (RBC) count, white blood cell (WBC) - total count, WBC differential reported as % and absolute values to include basophils, eosinophils, lymphocytes, monocytes, neutrophils.

BLOOD CHEMISTRIES:

Alanine aminotransferase (ALT), Alkaline Phosphatase (ALP), Aspartate aminotransferase (AST), Bicarbonate (HCO₃), Bilirubin (Total, Direct, Indirect), Blood Urea Nitrogen (BUN), Calcium (Ca), Chloride (Cl), Creatinine, Glucose, Magnesium

(Mg), Phosphorus (P), Potassium (K), Protein (Total), Sodium (Na), Uric Acid, Albumin

URINALYSIS:

Blood, Glucose, Ketones, Leukocyte Esterase, Microscopic Examination, Nitrites, pH, Protein

THYROID PANEL:

Free T3, Free T4, Thyroid stimulating hormone (TSH)

LIPID PANEL:

LDL-Cholesterol, HDL-Cholesterol, Total Cholesterol, Triglycerides

SEX HORMONES:

For females: estradiol, follicle-stimulating hormone (FSH), and luteinizing hormone (LH).

For males: testosterone.

URINE DRUG SCREENING:

Amphetamines, Barbiturates, Benzodiazepines, Cannabinoids, Cocaine, Methamphetamines, Methadone, Methylenedioxymethamphetamine (MDMA), Phencyclidine (PCP), Opiates, Oxycodone, Tricyclic Antidepressants

OTHER TESTS:

Breath Alcohol Test, Serum Pregnancy (B-hCG) (in female subjects only), Urine Pregnancy Test (in female subjects only)

Hematology, chemistry, urinalysis, thyroid panel, lipid panel, and sex hormones are collected at Open-label baseline, Week 14, Week 26 or ET, and the EOS Visit.

The laboratory results collected in conventional units will be converted to SI units, and the SI units will be used for all of the summaries and listings. Clinical laboratory test results (hematology, chemistry, urinalysis, thyroid panel, lipid panel, and sex hormones) and their changes from DB baseline and OL baseline will be summarized by DB treatment and overall, and by visits including the endpoint (Week 26 LOCF), using descriptive statistics. For hematology, chemistry lipid panel, thyroid panel, and sex hormone tests, result will also be categorized as “Normal”, “Low”, or “High” based on their normal ranges. For urinalysis results, tests will be classified as “Normal” or “Abnormal”. Shift tables comparing laboratory test results from baseline to Week 26

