12.4. URINE DRUG SCREENING

Urine drug screening tests are collected at Open-Label Baseline, Week 2, Week 6, Week 10, Week 14, Week 18, Week 22, Week 26, and at the EOS. The urine drug screening data will be presented in a data listing.

12.5. 12-LEAD ECG

Assessment of Standard 12-lead ECG are obtained at each clinic assessment during the study. A central ECG Standard 12-lead ECG will record heart rate (HR), PR interval, RR interval, QT interval, Bazett's corrected QT (QTcB), Fridericia's corrected QT interval (QTcF), and QRS duration. The overall ECG assessment will be centrally reported as "Normal", "Abnormal, Not Clinically Significant", or "Abnormal, Clinically Significant" with respect to relevant abnormalities.

Observed results of each ECG parameter, change from DB baseline, and change from OL baseline will be summarized by DB treatment and overall, and by visit using descriptive statistics.

The QTcF and QTcB results will be adjusted as follows:

$$QTcF = QT / \sqrt[3]{RR}$$

$$QTcB = QT / \sqrt[2]{RR}$$

Bazett's and Fridericia's corrected QT_c values will be classified as having QT_c prolongation according to the following conditions.

QTc Prolongation
QTc >460 msec

QTc Prolongation
Increase from double-blind baseline QTc \geq 60 msec
Increase from double-blind baseline QTc \geq 30 msec
Increase from open-label baseline QTc \geq 60 msec
Increase from open-label baseline QTc \geq 30 msec

The number and percentage of subjects with QTc prolongation using either of the two correction methods (Bazett's, Fridericia's) will be summarized by DB treatment and overall, and by visit.

A shift table comparing the overall ECG assessment from baseline to Week 26 or ET, and from baseline to EOS will be presented.

In addition, the markedly abnormal post-baseline ECG results will also be summarized for subjects with at least one markedly abnormal value during the treatment period. The summary will be completed by DB treatment and overall, and age groups (6 - < 8 years, 8 - < 12 years, 12 - < 16 years, and > 16 years), and overall using the age at the time of the individual assessment.

A listing of markedly abnormal values will be provided.

Criteria for markedly abnormal values, used in the SEP360-202 study, are presented in the table below. They will also be used for the SEP360-310 study summary.

ECG parameter (unit)	Age (years old)	Abnormally Low	Abnormally High
HR (bpm)	6 to <8	< 65	> 115
	8 to <12	< 55	> 110
	12 to <16	< 50	> 105
	\geq 16	< 50	> 100

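### The protocol plans the vital-signs shift table to end of study, but the SAP stops it at Week 26 LOCF, before the off-drug visit, and gives no reason

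*SAP*

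**What the plan says.** Protocol 15.3.6.4 (Vital Signs) states: "A shift table will be presented comparing shifts from the baseline visit to end of study". The same paragraph limits the count of markedly abnormal vital signs to the 26-week treatment period and plans a count of orthostatic hypotension at each time point. Protocol Table 4 defines End of Treatment ("The day that the subject receives protocol-defined last dose of the study drug") separately from End of Study ("The day that the subject completes the study per the study design"). Protocol 11.4.11.3 titles Visit 13E End of Study and collects vital signs and an ECG there. Section 7.1 places that visit 3 weeks (± 7 days) after the final dose.

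SAP 12.8 states: "A shift table will be presented comparing shifts from the baseline visit to Week 26 LOCF". SAP 6.2.3 defines what is carried forward. Its bracketed list of excluded data ends "and Withdrawal Period assessments) will be carried forward to the study endpoint", so withdrawal-period assessments are among the data left out. SAP 12.8 names no shift categories except BMI class.

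Two neighbouring sections help with the reading. SAP 12.5 shifts the overall ECG assessment to Week 26 or ET and, separately, "from baseline to EOS will be presented". For laboratory tests, protocol 15.3.6.2 says "Shift tables comparing laboratory test results from OL baseline to end of study will be presented", while SAP 12.2 says "Shift tables comparing laboratory test results from baseline to Week 26" LOCF.

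**The concern.** Long-term safety is the primary objective, and Visit 13E is the only scheduled off-drug visit with vital signs. A baseline-to-EOS shift would show how many children remain in, or have moved into, a high or low pulse or blood pressure category after stopping. A shift that ends at Week 26 LOCF cannot show this.

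The question has some background. Protocol 4.3 reports that in the adult study mean heart rate rose during treatment and follow-up, generally more at 8 mg/day than at 4 mg/day. That is a group mean in adults. It makes an off-drug check reasonable, but it is not evidence that a rise persists in children.

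**Working it through.** **1. Are the two endpoints different visits?**

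| Item | Protocol | SAP |
|---|---|---|
| End of the vital-signs shift | End of study (15.3.6.4) | Week 26 LOCF (12.8) |
| Timing | Visit 13E, Week 29, off drug (11.4.11.3) | Last treatment-period value (6.2.3) |
| Withdrawal-period data included | Yes, if end of study is Visit 13E | No |
| Overall ECG shift | Not specified in 15.3.6.3 | Week 26 or ET, and EOS (12.5) |

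Visit 13E falls 21 − 7 = 14 to 21 + 7 = 28 days after the last dose. An on-schedule Visit 13E is therefore always outside the 3-day limit that SAP 6.1 and 6.2.3 set for late unscheduled and ET values, and it is excluded by name as a withdrawal-period assessment. Vital signs are scheduled at Visits 2E to 10E (9 visits) and at 13E, so 13E is 1 of 10 post-baseline visits.

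**2. What is planned for Visit 13E?** In the SAP text (the table shells are not available):
- EOS is a by-visit summary point for observed values and changes (6.1, 12.8).
- Markedly abnormal vital signs are listed (12.8).
- QTc prolongation is counted by visit, and the overall ECG assessment is shifted to EOS (12.5).
- Adverse events with onset more than 3 days after the last dose have their own summary (12.1).
- Orthostatic hypotension is counted at each time point if protocol 15.3.6.4 is followed. SAP 12.8 defines it for any clinic assessment but does not restate the count.

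None of these places children in supine or standing pulse or blood pressure categories at Visit 13E against baseline.

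**3. Which baseline?** SAP 6.2.1 adds a third baseline for EOS assessments, the last on-treatment value. Take an invented child aged 11 or over, for whom the upper pulse limit is 120: DB baseline 95, last on-treatment value 125, EOS 122.
- From DB baseline: within limits to high, 122 − 95 = +27.
- From the last on-treatment value: high to high, 122 − 125 = −3.

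The persisting rise shows only against a baseline from before treatment. For children given dasotraline in the core study, the OL baseline is itself an on-drug value, so DB baseline is needed as well.

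**4. How many children might be in the high category?** The documents give no figures, so every mean, SD and change here is an assumption. With baseline mean m, mean change d, SD s and upper limit L, P(EOS ≥ L) = 1 − Φ((L − m − d)/s).

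| Measure (age) | L | m | d | s | z | Per 100 |
|---|---|---|---|---|---|---|
| Pulse (6-10) | 135 | 80 to 95 | +5 | 12 | 4.17 to 2.92 | 0.002 to 0.18 |
| Pulse (11 and over) | 120 | 80 to 95 | +5 | 12 | 2.92 to 1.67 | 0.18 to 4.8 |
| SBP (6-12) | 120 | 98 to 108 | 0 to +3 | 10 | 2.20 to 0.90 | 1.4 to 18 |
| DBP (6-12) | 80 | 58 to 68 | 0 to +3 | 8 | 2.75 to 1.125 | 0.3 to 13 |

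These use the absolute limit alone, because the change part of the criterion cannot classify a child at baseline. They describe the proposed panel, not cases lost from a planned count. If a cell is empty, the one-sided 95% upper bound is 1 − 0.05^(1/n): 1.5% for an assumed n = 200, and 0.9% for the planned maximum of 330.

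**The case against.** The strongest objection is that end of study may not mean Visit 13E. Table 4 defines a completed subject as one who took part through the last on-treatment visit, Week 26. The protocol synopsis plans shifts to end of study, as appropriate, straight after a list that includes Tanner staging and CSHQ, neither of which is collected at 13E. SAP 12.11 uses EOS for a Tanner assessment made at Week 26 or ET. The laboratory shifts change in the same way, which suggests a convention. Much of this stands: the term is loose, and a reader should not infer a proven breach of the protocol. Visit 13E nevertheless carries the title End of Study. Protocol 15.3.6.4 itself contrasts the 26-week treatment period with end of study within one paragraph, and SAP 12.5 separates Week 26 or ET from EOS. If a convention was intended, it is not stated.

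A second objection is that Visit 13E is already well covered. That also stands. A reader might infer that the off-drug data go unanalysed, but step 2 of the working shows otherwise. Clinically significant findings are also to be recorded as AEs, and the primary endpoint is unaffected.

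A reader might also infer that limiting marked-value counts to the treatment period departs from the protocol. It does not. For vital signs the limit matches protocol 15.3.6.4, and for ECG heart rate, PR and QRS the SAP adds a count that the protocol does not plan.

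Finally, the invented child in step 3 would already be counted on treatment (125 − 95 = +30, and at least 120). That is correct. The panel's contribution is to show whether the rise was still there off drug.

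**Conclusion.** The point holds in a limited form. The protocol's vital-signs shift to end of study, most naturally Visit 13E, becomes a shift to Week 26 LOCF in the SAP. That value contains no withdrawal-period assessment, and the change is not explained. What is lost is one off-drug categorical comparison of pulse and blood pressure. Data collection, the primary endpoint and the by-visit EOS summaries are intact.

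The conclusion rests on reading end of study as Visit 13E and on the SAP text without its table shells. The counts per 100 are illustrations and carry no weight in it. It is worth correcting because the correction is cheap and serves the study's main purpose.

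**What to change.** In SAP 12.8, keep the Week 26 LOCF shift and add a baseline-to-EOS panel for supine and standing pulse and blood pressure.
- Categories: low, within limits, high, by the absolute-value part of the existing age-specific limits.
- Baselines: show the panel from OL baseline and from DB baseline. Do not use the last on-treatment value that SAP 6.2.1 defines for EOS assessments.
- Denominator: subjects with both values, as SAP 12.8 already specifies for its shift table.

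If Week 26 LOCF was a deliberate choice, one sentence giving the reason would settle the discrepancy, and it could cover the laboratory shifts too.

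The cost is SAP wording and one more table panel, with many pulse cells near zero. The data are already collected.

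An optional addition, which the protocol does not require, is a post-treatment block in the markedly abnormal vital-sign and ECG heart rate, PR and QRS tables. It would cover values more than 3 days after the last dose, over subjects assessed in that period, with pulse and blood pressure change measured from DB baseline.
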